4. TRIAL DESIGN

This trial will be a multi-site, prospective, non-randomised cohort study. Participants will undergo a robotic assisted radical prostatectomy with bilateral intrafascial nerve-sparing. The LaserSAFE technique will be used to analyse the corresponding posterolateral surfaces of the prostate. In case a PSM is found which fulfils the criteria for secondary resection this will be carried out by the operating surgeon before the end of the procedure. All samples will be processed using standard FFPE that will act as the reference standard. Patients will be monitored according to the standard of care at each centre. Quality of life questionnaires will be collected at before surgery, at 3 and 12 months after surgery. An adaptive design will allow monitoring of accuracy metrics thought the trial and adjust secondary resection criteria to maximise nerve-sparing.

5. SAMPLING METHODS

The study will be conducted at UCLH and at least 1 other NHS centre. Participating centres will require first to have completed a site initiation visit and have experience using the Histolog Scanner as described in the training section. Potential participants will be screened from the patients referred for radical prostatectomy to the participating sites. Patient selection criteria are as follows:

5.1. Inclusion Criteria

- Patients diagnosed with clinically significant operable cT2-T3a N0 M0 PC.
- Medically fit to undergo RARP.
- Scheduled for robot-assisted RARP with a recommendation against intrafascial nerve sparing on at least 1 side based on multidisciplinary meetings informed by MRI, biopsy result and clinical factors.
- Ability to read English sufficiently to understand PIS and able to give informed consent.

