	
 • MRI informed very low likelihood for extra prostatic extension in the proximity of NVB (Based on EPE Likert 1 score or tumour away from the posterolateral areas of the prostate) • MRI informed high likelihood for extra prostatic extension in the proximity of NVB (based on Likert 5 score or bulging tumour on MRI T2 images) • Patients in whom preoperative imaging shows rectal involvement or seminal vesicle invasion in which nerve-sparing is deemed not feasible due to oncological safety concerns. • Patients who received previous treatment for prostate cancer: External beam radiotherapy, brachytherapy, focal therapy, chemotherapy.
Statistical methodology and analysis:	
Statistical analysis
 
The primary analysis will evaluate the sensitivity of LaserSAFE to diagnose positive surgical margins per side against the final paraffin analysis. Specificity and positive and negative predictive values will be reported. Measures of accuracy will be presented with 95% confidence intervals. A definitive protocol for statistical analysis will be finalised before recruitment is finished.

Funding & Other	
Funding:	UCLH Charity Number 7298
Other support:	SamanTree Medical SA
Key Study Contacts TBD	
Committees	TMG
Sub-contractors	None

KEY ROLES AND RESPONSIBILITIES

SPONSOR: The sponsor is responsible for ensuring before a study begins that arrangements are in place for the research team to access resources and support to deliver the research as proposed and allocate responsibilities for the management, monitoring and reporting of the research. The Sponsor also must be satisfied there is agreement on appropriate arrangements to record, report and review significant developments as the research proceeds, and approve any modifications to the design.

FUNDER: The funder is the entity that will provide the funds (financial support) for the conduction of the study. Funders are expected to provide assistance to any enquiry, audit or investigation related to the funded work.

CHIEF INVESTIGATOR (CI): The person who takes overall responsibility for the design, conduct and reporting of a study. If the study involves researchers at more than once site, the CI takes on the primary responsibility whether he/she is an investigator at any particular site.

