5.2. Exclusion Criteria

- Patients who received neo-adjuvant ADT.
- MRI informed very low likelihood for extra prostatic extension in the proximity of NVB (Based on EPE Likert 1 score or tumour away from the posterolateral areas of the prostate)
- MRI informed high likelihood for extra prostatic extension in the proximity of NVB (based on Likert 5 score or bulging tumour on MRI T2 images)
- Patients in whom preoperative imaging shows rectal involvement or seminal vesicle invasion in which nerve-sparing is deemed not feasible due to oncological safety concerns.
- Patients who received previous treatment for prostate cancer: External beam radiotherapy, brachytherapy, focal therapy, chemotherapy.

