6. TRIAL PROCEDURES

6.1. Pre-Intervention Assessments

6.1.1. RARP Planning Meeting

Eligibility for the trial will be determined during a preoperative planning meeting with a radiologist and a surgeon, who will use mpMRI images, clinical and biopsy information to give a recommendation on the grade of nerve sparing deemed safe by side, this can be based on a Likert scale for EPE or site-specific scale:

- Not eligible for the trial
 - EPE Likert 1 / Intrafascial nerve sparing recommended on both sides
 - EPE Likert 5 / Bulky disease on MRI, on both sides, nerve-sparing deemed futile
- Eligible for the trial:
 - Unilateral or bilateral EPE Likert 2, 3 or 4 / Interfascial or limited nerve sparing recommended

These criteria are based on the results of the NeuroSAFE study, where to detect EPE, mpMRI had a good predictive value in the extremes but in equivocal cases had poor sensitivity (14). The results of the LaserSAFE Feasibility study confirmed these findings (30), where EPE Likert 1 had 0% positivity vs EPE Likert 5 that had 100% positivity, as seen below:

[figure not shown]

Image-based mpMRI surgical planning is aimed to assist surgeons, but the surgeon's discretion will take precedence in case nerve sparing is deemed unsafe due to intraoperative findings.

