6.3.1.2. Lasersafe Technique

The LaserSAFE procedure is performed using an FCM called the Histolog[®] scanner developed by Samantree[®] which can be placed within the operating room. Histolog Scanner, Histolog Viewer, and accessories will be used according to the Instructions for Use. No modification to the CE-Mark/UKCA-Mark/FDA 510k clearance approved intended use will be made. The Histolog[®] scanner produces digital images with high, micrometre-range resolution and enables the visualization of tissue microstructures down to the cellular level. The microscope can image an area of 48x36 mm in approximately 60 seconds. Its operating principle is based on non-ionizing, low-power optical radiation (Laser) with a wavelength of 488±5 nm, and it uses a point illumination conjugated with a pinhole in front of the detector to eliminate out-of-focus signals.

The protocol of image acquisition is as follows: the prostate is cleaned using damp gauze and completely submerged in a solution that contains a photoreactive agent Histolog Dip[®] for 10 seconds. The specimen is rinsed with 0.9% NaCl solution, placed on the Histolog[®] scanner and lightly compressed using a mouldable weight. An initial live view scan confirms adequate positioning and stability of the specimen to avoid movement artefacts. If the preliminary scan is deemed satisfactory, a high-resolution digital image is acquired and stored in the microscope hard drive. The prostate is rotated to image the contralateral side. Once both posterolateral surfaces are imaged the prostate is placed in a container and fixed with formalin. Image acquisition takes less than 5 minutes. A pathologist will interpret the images on site or remotely depending on site specific requirements and complete a reporting case report form. The findings will be communicated directly to the surgeon.

Nerve sparing decisions will be guided by the result of the LaserSAFE technique.

The presence of cancer cells at the surface margin of the specimen will constitute a positive margin. Detailed results including the length of positive margin in 2 dimensions and multifocality, will be collected and included in the results.

In the presence of a posterolateral PSM, the performance of secondary resection (SR) of the ipsilateral neurovascular bundle (NVB) will be made if any of the following are present:

- (1) Multiple areas of PSM where the sum of each maximum dimension is >3 mm
- (2) any single PSM area >3 mm in maximum dimension

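### Per-side accuracy results pool sides already recommended for intrafascial sparing with the sides LaserSAFE is meant to open to sparing, which can overstate NPV for the latter

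*Protocol*

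**What the plan says.** Entry is decided for the man, through at least one side. Section 5.1 requires "Scheduled for robot-assisted RARP with a recommendation against intrafascial nerve sparing on at least 1 side", and section 6.1.1 accepts "Unilateral or bilateral EPE Likert 2, 3 or 4 / Interfascial or limited nerve sparing recommended". The planning meeting rules a man out as low risk only for "EPE Likert 1 / Intrafascial nerve sparing recommended on both sides".

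From then on both sides are handled alike. Section 4: "Participants will undergo a robotic assisted radical prostatectomy with bilateral intrafascial nerve-sparing". Section 6.3.1.2: "Once both posterolateral surfaces are imaged the prostate is placed in a container and fixed with formalin". The secondary-resection criteria in 6.3.1.2 apply to whichever side shows the margin.

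The Study Summary gives the unit of analysis: "The primary analysis will evaluate the sensitivity of LaserSAFE to diagnose positive surgical margins per side against the final paraffin analysis". It adds specificity, PPV and NPV. Section 9.6.3 lists those metrics for any positive margin and for margins above 3 mm, and lists positive-margin prevalence for the whole cohort. Neither place distinguishes the two kinds of side. The recommendation is nevertheless made by side in 6.1.1, and 9.6.1 lists the nerve-sparing recommendation as a baseline variable.

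**The concern.** Section 2 says LaserSAFE is meant to make sparing safe for men who would otherwise not receive it, and it names the missed positive margin as the critical error. The figure a surgeon will want is therefore the chance that a negative scan is wrong on a side that would not otherwise have been spared intrafascially, which is 1−NPV on index sides.

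A man with a recommendation against intrafascial sparing on one side only also contributes a side on which it was already recommended. If positive margins are rarer there, those sides add mainly true negatives. The pooled NPV then looks better, and the pooled prevalence lower, than on the index sides. A reader could carry the pooled NPV over to index sides and underestimate the risk.

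**Working it through.** **Inputs from the protocol (9.3).** Expected sensitivity is 91% and positive-margin prevalence 20%. The stated sample size reproduces: 1.96² × 0.91 × 0.09 / 0.05² = 125.85, so 126; 126 / 0.20 = 630; 630 × 1.10 = 693. Section 9.3 counts participants, so using 20% as a per-side prevalence is an assumption.

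**Assumed inputs (not in the protocol).**
- 40–60% of men qualify on one side only. Each has one non-index side of two, so the non-index share of sides is s = 0.20 to 0.30.
- Index sides: prevalence 0.20, specificity 0.90.
- Non-index sides: prevalence p = 0 to 0.02; specificity c = 0.90 (equal) or 0.96 (easier negatives).
- Sensitivity is 0.91 on every side.

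**Index sides alone.** FN = 0.20 × 0.09 = 0.018; TN = 0.80 × 0.90 = 0.72; TP = 0.182; FP = 0.08.
- 1−NPV = 0.018 / 0.738 = 2.44%
- PPV = 0.182 / 0.262 = 69.5%

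**Pooled.** FN = (1−s) × 0.018 + s × p × 0.09, and TN = (1−s) × 0.72 + s × (1−p) × c. For s = 0.20, p = 0, c = 0.90: FN = 0.0144, TN = 0.576 + 0.18 = 0.756, so 1−NPV = 0.0144 / 0.7704 = 1.87%. The other cases follow in the same way:

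| s | p | 1−NPV, c = 0.90 | 1−NPV, c = 0.96 | Prevalence |
|---|---|---|---|---|
| 0.20 | 0 | 1.87% | 1.84% | 16.0% |
| 0.20 | 0.02 | 1.92% | 1.89% | 16.4% |
| 0.30 | 0 | 1.60% | 1.57% | 14.0% |
| 0.30 | 0.02 | 1.68% | 1.64% | 14.6% |

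Pooled 1−NPV is 0.5 to 0.9 percentage points below the index-side figure, or 21–36% lower in relative terms. Nearly all of this comes from prevalence; the specificity assumption hardly matters.

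**Other index-side prevalences.** With p = 0 and c = 0.90:
- At 10%, index 1−NPV = 0.009 / 0.819 = 1.10%. Pooled, it is 0.0072 / 0.8352 = 0.86% (s = 0.20) or 0.0063 / 0.8433 = 0.75% (s = 0.30).
- At 30%, index 1−NPV = 0.027 / 0.657 = 4.11%. Pooled at s = 0.25, it is 0.02025 / 0.71775 = 2.82%.

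**The other metrics.**
- Specificity: with c = 0.90 it stays at 90%. With c = 0.96 and p = 0 it becomes 0.768 / 0.84 = 91.4% (s = 0.20) or 0.792 / 0.86 = 92.1% (s = 0.30). The gain is the assumption itself.
- PPV, p = 0: with c = 0.90 it falls from 69.5% to 0.1456 / 0.2296 = 63.4% (s = 0.20) or 0.1274 / 0.2134 = 59.7% (s = 0.30). With c = 0.96 it falls to 66.9% or 65.2%.
- Sensitivity: at p = 0.02, non-index sides hold only 0.004 / 0.164 = 2.4% (s = 0.20) to 0.006 / 0.146 = 4.1% (s = 0.30) of the positive sides. At p = 0 they hold none.

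**The case against.** **The low prevalence on non-index sides is not established.** Section 6.1.1 reports "where EPE Likert 1 had 0% positivity vs EPE Likert 5 that had 100% positivity", but that sentence follows one about MRI detecting extraprostatic extension, so positivity may mean extension rather than a positive margin. Section 2 also says that dissecting closer to the capsule raises margin risk, and every side here is meant to be dissected intrafascially. A non-index side need not be Likert 1 either, because site-specific scales and clinical information are allowed. This stands: lower prevalence is plausible, but its size is unknown.

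**The eligibility text is not consistent.** Section 5.2 excludes "MRI informed very low likelihood for extra prostatic extension in the proximity of NVB" without saying whether one side is enough, whereas 6.1.1 attaches both sides to the low-risk exclusion. Read literally, 5.2 could remove many of the men in question. Section 6.1.1 likewise excludes Likert 5 only when bilateral. A contralateral Likert 5 side could then enter and push NPV down: if 10% of men had one and all such sides were positive, with every other side at the index values, 1−NPV would be 0.0432 / 1.4112 = 3.1%. So the direction of the pooled error is not certain, which is a further reason to show the sides separately.

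**Stronger readings that a reader might infer.**
- *Pooling inflates specificity.* Specificity does not depend on prevalence, and no section gives it by side.
- *Pooling flatters every metric.* PPV may fall.
- *The residual-tumour rate that moves the cut-off in 9.2 is wrong because it mixes sides.* The resection rule applies to both sides, so a pooled rate is a legitimate basis for it.
- *Only index sides belong to the trial's question.* A positive scan can cost a nerve bundle on either side, so accuracy on non-index sides is also part of the intended use.

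**It could be left to the analysis plan.** The per-side unit appears only in the Study Summary, a definitive statistical protocol is promised, and nothing prevents a split. That keeps the point modest. The protocol does, however, itself fix bilateral imaging, the per-side summary and the list of metrics.

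**Conclusion.** The point holds for NPV and positive-margin prevalence. Men qualify through one side, both sides enter a per-side analysis, and the protocol does not separate sides already recommended for intrafascial sparing. If positive margins are rarer on those sides, the pooled NPV is too favourable for the sides whose sparing decision LaserSAFE is meant to change. Under the assumptions above, 1−NPV is 2.4% on index sides and about 1.6–1.9% pooled, and prevalence is 20% against 14–16.4%.

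The one-sided share, the prevalence by side type and the specificity are assumptions, so these figures illustrate the effect rather than estimate it. The documents do not support a claim that specificity is inflated, that the adaptive cut-off rule is invalid, or that the primary endpoint is compromised. This is a worthwhile improvement to secondary reporting.

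**What to change.** 1. In 9.6.3, define index sides as those with a pre-operative recommendation against intrafascial sparing. Report sensitivity, specificity, PPV, NPV and positive-margin prevalence for index sides and for non-index sides, next to the all-sides figures.
2. Base any statement about the safety of a negative scan on an otherwise unspared side on the index-side NPV.
3. Show the residual-tumour rate in secondary resections by side type as a descriptive row, leaving the adaptive rule in 9.2 as it is.
4. Reconcile 5.2 and 6.1.1 on whether Likert 1 or Likert 5 on one side only excludes a man.

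No new data or participants are needed, because the recommendation is already made by side and recorded; the CRF should hold it by side. The cost is a slightly less favourable NPV and slightly wider intervals for index sides. For specificity, index sides hold 0.64 / 0.84 = 76% to 0.56 / 0.86 = 65% of the margin-negative sides (p = 0), so at equal specificity the interval is about 1/√0.76 = 1.15 to 1/√0.65 = 1.24 times as wide.

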5.2. Exclusion Criteria

- Patients who received neo-adjuvant ADT.
- MRI informed very low likelihood for extra prostatic extension in the proximity of NVB (Based on EPE Likert 1 score or tumour away from the posterolateral areas of the prostate)
- MRI informed high likelihood for extra prostatic extension in the proximity of NVB (based on Likert 5 score or bulging tumour on MRI T2 images)
- Patients in whom preoperative imaging shows rectal involvement or seminal vesicle invasion in which nerve-sparing is deemed not feasible due to oncological safety concerns.
- Patients who received previous treatment for prostate cancer: External beam radiotherapy, brachytherapy, focal therapy, chemotherapy.

5.3. Recruitment

Eligible patients will be identified at each centre during a preoperative multidisciplinary meeting where candidates for RARP based on a diagnosis of localised PCa are referred. Special emphasis will be made to recruit patients with good erectile function who have a recommendation against intrafascial nerve sparing on at least 1 side. To ensure diversity and equity in patient representation, we will actively encourage the recruitment of individuals from Black, Asian, and minority ethnic groups. We have previously worked with charities and focus groups aimed at increasing participation of Black African and Afro-Caribbean patient populations in research and will continue to do so during the recruitment phase of this study. Furthermore, we will closely monitor the proportion of patients recruited from these communities and if necessary adjust recruitment strategies by reaching out to community support groups.

Participant recruitment at a site will only commence when the trial has:

- Been confirmed by the Sponsor (or it's delegated representative), and
- Been issued with Confirmation of Capacity and Capability from each participating site.

Once a potential participant has been identified, they will be approached via telephone before the planned surgery date and eligibility for the study will be confirmed. If interested, they will receive a patient information sheet (PIS) sent via NHS email or post.

5.4. Informed Consent

Potential participants will be seen in person or called by a designated member of the research team to obtain informed consent within a week of patients receiving a PIS. Adequate explanation of the aims, methods, anticipated risks and potential benefits of participating in the study will be given. The investigator will explain that participants are under no obligation to enter the trial and that they can withdraw at any time during the trial, without having to give a reason and without prejudicing his/her further treatment. No trial procedures, including the collection of identifiable participant data will be conducted prior to the participant giving consent by signing the consent form. Consent will not denote enrolment into trial.

If they verbally consent to be enrolled in the study, participants will sign a paper consent form if seen face to face or a secure electronic consent form if approached via phone call. The electronic consent platform will be developed within the RedCAP service hosted behind the UCL Data Safe Haven, which conforms to NHS Data Security & Protection Toolkit, General Data Protection Regulation, and ISO 27001 Information Security. We have previously used a similar E-Consent method during the NeuroSAFE PROOF study and LaserSAFE feasibility study.

A copy of the consent form will be given to the patient, a copy uploaded to the electronic health records of the patient and the original will be stored in the ISF. All members of the team consenting patients will be suitably qualified, experienced, and will have been delegated this duty by the CI/ PI on the Staff Signature and Delegation of Tasks.

It will be recorded in the patient medical notes (or electronic health record system) when the participant information sheet (PIS) has been given to the participant.

The PIS and consent form will be reviewed and updated if necessary, throughout the trial according to analysis of thresholds to define secondary resection of periprostatic tissue and participants will be re-consented as appropriate.

6. TRIAL PROCEDURES

6.1. Pre-Intervention Assessments

6.1.1. RARP Planning Meeting

Eligibility for the trial will be determined during a preoperative planning meeting with a radiologist and a surgeon, who will use mpMRI images, clinical and biopsy information to give a recommendation on the grade of nerve sparing deemed safe by side, this can be based on a Likert scale for EPE or site-specific scale:

- Not eligible for the trial
 - EPE Likert 1 / Intrafascial nerve sparing recommended on both sides
 - EPE Likert 5 / Bulky disease on MRI, on both sides, nerve-sparing deemed futile
- Eligible for the trial:
 - Unilateral or bilateral EPE Likert 2, 3 or 4 / Interfascial or limited nerve sparing recommended

These criteria are based on the results of the NeuroSAFE study, where to detect EPE, mpMRI had a good predictive value in the extremes but in equivocal cases had poor sensitivity (14). The results of the LaserSAFE Feasibility study confirmed these findings (30), where EPE Likert 1 had 0% positivity vs EPE Likert 5 that had 100% positivity, as seen below:

[figure not shown]

Image-based mpMRI surgical planning is aimed to assist surgeons, but the surgeon's discretion will take precedence in case nerve sparing is deemed unsafe due to intraoperative findings.

6.2. Registration Procedures

Participant registration will be undertaken centrally by the coordinating trial team/remotely at sites using RedCAP. Each patient will be assigned a unique ID, and this ID will be used for identifying the patient. All LaserSAFE images will be pseudo-anonymised using this ID. Completed consent forms will be stored in the ISF in a locked cabinet for secure storage. Patient identifiable data and the above clinical data will be held securely in a database Data Safe Haven RedCAP service.

6.3. Baseline and Intervention Procedures

6.3.1. Baseline Data

The following clinical data will be collected for each patient by the CRF:

- Age
- Preoperative function using EPIC-26 questionnaire
- Prostate biopsy histology report
- Clinical stage
- Prostate Specific Antigen (PSA) before surgery
- Imaging results (mpMRI)
- LaserSAFE results
- Final paraffin embedded analysis results
- PSA results up to 12 months of follow-up
- Additional postoperative therapies

Table 2. Patient recruitment, sample collection and follow-up procedure

Procedure	Screening/Baseline	Recruitment	Treatment	Pathology review	3 months	12 months
Eligibility assessment	x					
Approaching patients		x				
Informed Consent		x				
Quality of life questionnaire (EPIC-26)		x			x	X
RARP and LaserSAFE			x			
Medical record review			x	x	x	x

